Appendix B

Facilities & Equipment

[figure not shown]
The Aging in Place apartment simulates a real-life apartment dwelling. The stroke survivor will be connected to the Oculus Quest VR in the living room area in front of the television. The television on the wall will be used to project the user's activities on the Oculus Quest Virtual Reality System so that the therapist(s) and caregiver can provide feedback during the rehabilitation sessions. There is a camera in the living room that can be accessed using a HIPAA-compliant technology web-based application.

Each member of the Investigative Team has dedicated office space equipped with computers, printers, scanners, and projectors to support study meetings as well as access to needed software (e.g., R, SAS, etc.). The team space is equipped with white boards, phone conferencing, and video-conferencing capabilities. Study staff have access to work-issued office phones, desktop computers, and laptops as needed. Conferencing software (e.g., WebEx) and support is available to all UTHealth employees.

[figure not shown]
Each office is equipped with a desk, filing cabinets, dual processor PC computer, phone, and access to fax machines, printers (both black and white and color LaserJet), photocopiers, and scanners. The Center for Nursing Research provides secretarial, accounting, editorial, library, and administrative support to all faculty members and supportive staff. University provided secure server space and SecureStor for secure email will be provided. All software needed for machine learning and secure server space for “big data” projects are provided by UTHealth. Information Technology teams are available for support.

Appendix C

A. Gourmet Chef

B. Office Worker

Examples of the Job Simulator Games. The white gloves in the pictures are the user's hands that are directed by the user's hand game controls that will be used for gross upper extremity rehabilitation. The user can interact with the environment such as cooking on the stove in a kitchen (A) or using a computer or telephone in an office (B). The floating computer with a face interacts with the user to provide a sequence of instructions on how to interact in the virtual environment (e.g., make a sandwich) and uses aspects of cognitive rehabilitation such as planning, sequencing, judgement, and memory.

Appendix D

Cues to be Given to the Stroke Participant by the Caregiver

Helpful Tips to Encourage Partner:

- Summarize instructions and have partner repeat prior to starting the session
- Speak slowly and clearly in simple sentences – don't talk down or use "baby talk"
- Use animation/emotion while talking
- Speak how you expect to be spoken to – be a good model
- Focus on the positive
- Encourage positive self-talk phrases such as "I can do this if I take my time."
- Encourage saying steps aloud to stay on task and stay focused

If partner is getting frustrated or confused:

- Prior to giving complete direction, ask leading questions such as:
 - "Did you look all the way to the right? Was there anything on the bottom shelf that could help you heat the tea? Can you show me where WE keep the _____ (e.g., cheese for cooking task), look in there."
- If partner has difficulty expressing what they need or are frustrated about:
 - Establish topic first - For example: "Is this about the activity? No. Is it about a person? Yes. A family member?"
- Give as much assistance as is required to ensure good comprehension and for your loved one to remain relaxed:
 - reword
 - prompt
 - gesture
 - point
 - encourage
 - smile
 - give time for responses
 - try to let partner answer as much as possible
- If they become upset, check whether they wish to stop and take a brief break
- If more frustrated than normal, check:
 - Pain
 - Hunger/thirst
 - Fatigue
 - Emotions/worries
 - Room/temperature
- Focus on the positive
- Reassure them that any positive or negative feelings are valid
- If the experience has caused any distress, reassure them that there will be improvement from where they are today
- Discuss what will happen in next session including how you might deal with any issues – write these down to discuss with therapist
- Take notes on any questions you may have for therapist at next session. Consider discussing with each other, writing down, and discussing with therapist: "What helps?" and "What makes it harder?"

Appendix E

Therapeutic Guided Cues Protocol^{12,13} for the Stroke Survivor Participants to be Used by the Research Assistant .

During the session:

Problem solving:

- What will you gain by doing exercises at today's session?
- (Reinforce with the patient) Flexible coping strategies include:
 - define the problem and goal
 - generate multiple solutions
 - select a solution
 - implement and evaluate

Decision making:

- What will you do if you start to feel dizzy or not well during today's session?

Resource utilization:

- How will you seek assistance from your caregiver today during the session?
- You can ask me to assist you during the session. How will you signal to me that you want to stop?

Partnership with rehabilitation therapist/ RA:

- Do you understand what I am asking you to do?
- Would you like to practice the arm/ hand movements (or using the hand controller) with me before starting the session?

Planning and taking action:

- How will you use the hand controller?
- How will you put the headset on? Who will assist you?
- How many times this week will you come to the AIP apartment for your rehabilitation session?

For arm/ hand exercises at home:

Problem solving:

- What will you gain by doing arm/ hand exercises at home?

Decision making & Planning and taking action:

- Where/ when/ what/ how will you do your arm/ hand exercises?
- How will you know if you are doing your arm/ hand exercises correctly?
- How will you know when to stop doing your hand/ arm exercises?

Resource utilization:

- Can a friend or family member assist you with your arm/ hand exercises?
- Do you have a non-slippery surface at home where you can do your exercises?
- Do you have slip-resistant shoes?

Appendix F
Burden Scale for Family Caregivers – short version

We are asking you for information about your present situation. The present situation comprises your caregiving deduced from the illness of your family member (or friend).

The following statements often refer to the type of your assistance. This may be any kind of support up to nursing care.

Please draw an "X" for the best description of your present situation.
Please answer every question!

	strongly agree	agree	disagree	strongly disagree
1. My life satisfaction has suffered because of the care.				
2. I often feel physically exhausted.				
3. From time to time I wish I could "run away" from the situation I am in.				
4. Sometimes I don't really feel like "myself" as before.				
5. Since I have been a caregiver my financial situation has decreased.				
6. My health is affected by the care situation.				
7. The care takes a lot of my own strength.				
8. I feel torn between the demands of my environment (such as family) and the demands of the care.				
9. I am worried about my future because of the care I give.				
10. My relationships with other family members, relatives, friends and acquaintances are suffering as a result of the care.				

Appendix G
System Usability Scale (SUS)

	Strongly Disagree	Disagree	Neither Agree nor Disagree	Agree	Strongly Agree
I think that I would like to use this headset frequently					
I found this headset unnecessarily complex					
I thought this headset was easy to use					
I think that I would need assistance to be able to use this VR experience					
I found the various functions in this headset were well integrated					
I thought there was too much inconsistency in the headset					
I would imagine that most people would learn to use this headset very quickly					
I found the headset very cumbersome/awkward to use					
I feel confident using the headset					
I needed to learn a lot of things before I could get going with this headset					

Appendix H

Presence Questionnaire Version 3 (RedCap)

Version 3 of the PQ uses a seven-point Likert-type scale, although response choices differ slightly for each item stem (e.g., for item 2, 1 = “not responsive,” 7 = “very responsive;” for item 7, 1 = “not compelling,” 7 = “very compelling”). The 29 items are divided into four components as follows:

Involved

1. How much were you able to control events?
2. How responsive was the environment to actions that you initiated (or performed)?
3. How natural did your interactions with the environment seem?
4. How much did the visual aspects of the environment involve you?
5. How natural was the mechanism which controlled movement through the environment?
6. How compelling was your sense of objects moving through space?
7. How much did your experiences in the virtual environment seem consistent with your real-world experiences?
8. How completely were you able to actively survey or search the environment using vision?
9. How compelling was your sense of moving around inside the virtual environment?
10. How well could you move or manipulate objects in the virtual environment?
11. How involved were you in the virtual environment experience?
12. How easy was it to identify objects through physical interaction, like touching an object, walking over a surface, or bumping into a wall or object?

Sensory Fidelity

13. How much did the auditory aspects of the environment involve you?
14. How well could you identify sounds?
15. How well could you localize sounds?
16. How well could you actively survey or search the virtual environment using touch?
17. How closely were you able to examine objects?
18. How well could you examine objects from multiple viewpoints?

Adaptation/Immersion

19. Were you able to anticipate what would happen next in response to the actions that you performed?
20. How quickly did you adjust to the virtual environment experience?

21. How proficient in moving and interacting with the virtual environment did you feel at the end of the experience?
22. How well could you concentrate on the assigned tasks or required activities rather than on the mechanisms used to perform those tasks or activities?
23. How completely were your senses engaged in this experience?
24. Were there moments during the virtual environment experience when you felt completely focused on the task or environment?
25. How easily did you adjust to the control devices used to interact with the virtual environment?
26. Was the information provided through different senses in the virtual environment (e.g., vision, hearing, touch) consistent?

Interface Quality

27. How much delay did you experience between your actions and expected outcomes?
28. How much did the visual display quality interfere or distract you from performing assigned tasks or required activities?
29. How much did the control devices interfere with the performance of assigned tasks or with other activities

[figure not shown]
[figure not shown]
Appendix I
Simulator Sickness Questionnaire (SSQ)

Simulator Sickness Questionnaire (SSQ) items

SSQ items	Likert Scale		
	Slight	Moderate	Severe
General Discomfort			
Fatigue			
Headache			
Eyestrain			
Difficulty Focusing			
Increased Salivation			
Sweating			
Nausea			
Difficulty Concentration			
Fullness of Head			
Blurred Vision			
Dizziness (eye open)			
Dizziness (eye closed)			
Vertigo			
Stomach Awareness			
Burping			

Appendix J

Montreal Cognitive Assessment (MoCA)

MONTREAL COGNITIVE ASSESSMENT (MOCA)		NAME : _____	Education : _____	Date of birth : _____	Sex : _____	DATE : _____									
VISUOSPATIAL / EXECUTIVE 			Copy cube  [] Contour  [] Numbers  [] Hands	Draw CLOCK (Ten past eleven) (3 points)	_____ / 5										
NAMING 		_____ / 3													
MEMORY Read list of words, subject must repeat them. Do 2 trials. Do a recall after 5 minutes.		
 
 1st trial	FACE	VELVET	CHURCH	DAISY	RED	
 
 2nd trial						
 
	1st trial	FACE	VELVET	CHURCH	DAISY	RED	2nd trial						No points
1st trial	FACE	VELVET	CHURCH	DAISY	RED										
2nd trial															
ATTENTION Read list of digits (1 digit/sec). Subject has to repeat them in the forward order  [] 2 1 8 5 4 Subject has to repeat them in the backward order  [] 7 4 2		_____ / 2													
Read list of letters. The subject must tap with his hand at each letter A. No points if 2 or more errors  [] F B A C M N A A J K L B A F A K D E A A J A M O F A A B		_____ / 1													
Serial 7 subtraction starting at 100  [] 93  [] 86  [] 79  [] 72  [] 65 4 or 5 correct subtractions: 3 pts, 2 or 3 correct: 2 pts, 1 correct: 1 pt, 0 correct: 0 pt		_____ / 3													
LANGUAGE Repeat: I only know that John is the one to help today.  [] The cat always hid under the couch when dogs were in the room.  []		_____ / 2													
Fluency / Name maximum number of words in one minute that begin with the letter F  [] _____ (N ≥ 11 words)		_____ / 1													
ABSTRACTION Similarity between e.g. banana - orange = fruit  [] train - bicycle  [] watch - ruler		_____ / 2													
DELAYED RECALL Has to recall words WITH NO CUE  [] FACE  [] VELVET  [] CHURCH  [] DAISY  [] RED  []		Points for UNCUED recall only  []	_____ / 5												
Optional Category cue  [] Multiple choice cue  []  [] Date  [] Month  [] Year  [] Day  [] Place  [] City		_____ / 6													
© Z.Nasreddine MD Version November 7, 2004 www.mocatest.org		Normal ≥ 26 / 30 TOTAL _____ / 30 Add 1 point if ≤ 12 yr edu													

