 - Stroke survivors will be excluded if they do not have score ranges that indicate mild to moderate severity on prior post-stroke neuropsychological tests, or the MoCA (15-25) using normative data based on education, age, and other standard demographic data, or other appropriate cognitive screening test selected by the speech language pathologist (also on this application) if the participant has aphasia, hemiopsia, other neurological or specific cognitive deficits, or demographic factors (e.g., education level) that prevents the participant from being accurately examined using MoCA or a modified MoCA; if cognition is within normal range then a FM (20-50), if they are unstable while standing unassisted, have a history of motion sickness/ vertigo/ dizziness/ seizures (a doctor's note will be requested for participants who do not believe their seizures will be triggered by the VR), claustrophobia, blind/deaf, and cannot hold the controller in their affected arm with or without the use of assistance.

Study Design/Methods

[figure not shown]

Figure 1: Study Schema

- Figure 1 depicts the overall study schema or flow as described below.

- Study Overview:
 - **S.A.1.** With the current drive for telerehabilitation and the advent of VR headsets, the examination of human factors perspectives is necessary before full implementation. End user perspectives regarding the impact, perceived usefulness, and perceived ease of use are essential, particularly in the older stroke population.
 - **S.A.2.** The rehabilitation team will measure changes on standardized measurements as part of standard of care.
 - **S.A.3.** Understanding the role of caregiver engagement upon stroke survivor rehabilitation outcomes and its potential impact on the quality of dyadic interpersonal relations is imperative for the sustainability of using VR for stroke rehabilitation in the home.
- Recruitment:
 - We will recruit 20 stroke survivor dyads (n=40) from the
 - Place: UT Physicians Department of Neurology Stroke Clinic, Brain and Behavioral Health Clinic, TIRR, Memorial Hermann, and Stroke Survivor Support Groups. In 2021, the clinic treated approximately 1000 stroke patients. Based on our knowledge of the clinic and previous experiences with stroke trial enrollment, enrolling 20 dyads over a 6-month recruitment period will be feasible. All rehabilitation sessions will take place in the Aging in Place (AIP) apartment.

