- To address S.A.2. As part of standard of care, we will calculate change in arm and cognitive scores for each stroke participant from the following tests: MoCA, FM, and ARAT. (See Appendix J, K, and L) After inspection of the distribution, either the paired t-test or the nonparametric Wilcoxon signed rank test will be used to evaluate the significance of the difference score. However, statistical inference is not the primary interest of this pilot study. The effect size provided by Cohen's d measure, i.e., the standardized difference of mean score, will provide a preliminary measure of the effectiveness of Oculus VR in this pilot study. Similarly, standardized differences in the BSFC-s scores will provide the effect sizes for the change in caregiver burden.
- To address S.A.3., interview data will be analyzed following methods for thematic analysis.^{34,35} Using a qualitative data analysis program, Atlas.ti,³⁶ 2 researchers will review transcripts to gain a sense of the whole, identify codes, categories, and generate higher order themes to describe

the role of caregiver engagement during the session. Reasons for non-participation will be obtained from those eligible participants who decline participation. Unacceptable components and reasons for non-participation will be considered in the planning and designing of future trials.

Outcomes

- Upon completion of these aims, the expected outcomes are to develop randomized control trials (RCTs) to determine the effectiveness of the Oculus VR for stroke rehabilitation. We anticipate using the information from the dyadic interviews to develop qualitative studies and RCTs examining the role of the caregiver on remote stroke rehabilitation outcomes.
- Please see Table 1 (below) for the outcomes with timepoints.

Primary and Secondary Outcomes with Timepoints			
Primary	Timepoint	Secondary	Timepoint
MoCA (Appendix J)	Baseline and Last Session	Pre-Intervention Questionnaire (Appendix R)	Baseline Session
Fugl-Meyer (Appendix K)	Baseline and Last Session	Therapy Follow-Up Checklist (Appendix M)	Session 2 – Last Session
ARAT (Appendix L)	Baseline and Last Session	Post-Intervention Questionnaire (Appendix S)	Last Session
Caregiver Burden Scale (for caregiver only; Appendix F)	Baseline and Last Session		
Simulator Sickness Questionnaire (Appendix I)	Session 1 – Last Session		
System Usability Scale (Appendix G)	Last Session		
Presence Questionnaire (Appendix H)	Last Session		

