Appendix Q
Timeline of Study Events with Outcome Measures and Timepoints

BASELINE (Video Call or in person)	Initial & Date completed
Informed Consent documents will be available in English. The consent form will be accessible via REDCap. This visit is to ensure the participant understands the basis of this voluntary study and provides consent to participate in the research study.	
Pre-First Visit (Video Call or in person at 1 st visit)	
We will ask the stroke survivor about their medical history and give the stroke survivor the Montreal Cognitive Assessment (MoCA) or other appropriate cognitive screening test if the participant has aphasia, hemiopsia, and other neurological deficits that cannot be examined using MoCA or a modified MoCA that will assess their cognitive capabilities. We will arrange a time to meet with the stroke survivor and their caregiver on a video call using the computer and this will take only 15 or 20 minutes. We will offer the option to complete the Pre-Intervention Questionnaire of the stroke survivor participant and Burden Scale for Family Caregivers depending on participant and caregiver preferences. This will take 15-20 additional minutes. F	

 1. Assess stroke survivor's medical history 2. Cognition (MoCA) test completed (Appendix J) 	
Inclusion Criteria	

Patients must meet the following criteria for study entry:
 
 • Ischemic, hemorrhagic, or SAH stroke diagnosis within 6 months to 5 years of enrollment. • Dyads will be included if they 
 ◦ Are \geq 18 years old ◦ Can read, write, comprehend ◦ Speak English ◦ Are willing and able to provide informed consent • Caregivers must live in the home with the stroke survivor. 	
Exclusion Criteria	
General	

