
 • Stroke survivors will be excluded if they do not have score ranges that indicate mild to moderate severity on prior post-stroke neuropsychological tests, or the MoCA (15-25) using normative data based on education, age, and other standard demographic data, or other appropriate cognitive screening test selected by the speech language pathologist (also on this application) if the participant has aphasia, hemiopsia, other neurological or specific cognitive deficits, or demographic factors (e.g., education level) that prevents the participant from being accurately examined using MoCA or a modified MoCA; if cognition is within normal range then a FM (20-50) • Have a history of: 
 ◦ Motion sickness ◦ Vertigo ◦ Dizziness ◦ Seizures (a doctor's note will be requested for participants who do not believe their seizures will be triggered by the VR) ◦ Claustrophobia ◦ Blind/deaf • Cannot hold the controller in their affected arm. 	

	IRB NUM: ER: HSC-SN-22-08 8
	IRB APPROVAL DATE: 03/06/2024

1st Session (Week 1)	Initial & Date completed

3. Pre-Intervention Questionnaire will be given during the first session. (Appendix R)
 
4. Cognition (MoCA or other appropriate) test completed (if not completed during pre-first visit) (Appendix J)
 
5. Fugl-Meyer Upper Extremity Assessment (Appendix K)
 
6. Action Research Arm Test (ARAT) (Appendix L)
 
a. 3,4, and 5 will be completed as a part of standard of care.
 
7. Burden Scale for Family Caregivers – short version will be given to the caregivers of the stroke subjects via REDCap. (Appendix F)
	
 Recruit from stroke units/clinics	
 Study coordinator screens for eligibility requirements	
 Obtain Informed Consent Documents from Dyads	
 Complete the Cognition (MoCA) test (pre-intervention) (Primary Outcome; Appendix J)	
 Complete the Fugl-Meyer Upper Extremity Assessment (pre-intervention) (Primary Outcome; Appendix K)	
 Complete the Action Research Atm Test (ARAT) (pre-intervention) (Primary Outcome; Appendix L)	
 Have the Caregivers complete the Burden Scale for Family Caregivers (Primary Outcome; Appendix F)	

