We will give the stroke survivor the Montreal Cognitive Assessment (MoCA) that will assess their cognitive capabilities. We will arrange a time to meet with them on a video call using the computer and this will take only 15 or 20 minutes.	
1. Cognition (MoCA) test completed (Primary Outcome; Appendix J)	
12th Session (Week 4, last session; in the event that the study participant and/ or caregiver are unable to complete any post-intervention items, we will request a video call to complete any missing items that were not completed on the last session at a time convenient to the stroke participant or caregiver)	Initial & Date completed

 _____ Research Assistant complete the Therapy Follow Up Checklist with Subject before the start of the session. (Secondary Outcome, Appendix M) _____ Have the stroke survivor complete the Simulator Sickness Questionnaire (SSQ) at the beginning and end of the last 1-hour session (Primary Outcome; Appendix I) _____ Complete the System Usability Survey (SUS) via REDCap (Primary Outcome; Appendix G) _____ Complete the Presence Questionnaire (PQ) (Primary Outcome; Appendix H) 	

 Complete the Cognition (MoCA) test (post-intervention, if not completed during the Pre-Last Visit) (Primary Outcome; Appendix J)	
 Complete the Fugl-Meyer Upper Extremity Assessment (post-intervention) (Primary Outcome; Appendix K)	
 Complete the Action Research Atm Test (ARAT) (post-intervention) (Primary Outcome; Appendix L)	
 Complete the Caregiver Burden Questionnaire (Primary Outcome; Appendix F)	
 Complete the Post-Intervention Questionnaire (Participant and Caregiver) (Secondary Outcome; Appendix S)	

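### One MoCA form is cited for both assessments in an uncontrolled study, so any retest gain cannot be separated from cognitive improvement, yet the plan reads Cohen's d of the change as effectiveness

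*Combined protocol and SAP*

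**What the plan says.** Appendix J reproduces one MoCA form, dated November 2004. Its content is fixed: five named words, set drawings, digit strings, sentences and word pairs. The instruction for the words is "Read list of words, subject must repeat them. Do 2 trials. Do a recall after 5 minutes". They are scored later under delayed recall ("Has to recall words WITH NO CUE"), which carries 5 of the 30 points.

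The same appendix is cited at both time points. Table 1 lists the MoCA, with Appendix J, as a primary outcome at baseline and last session. The Appendix Q checklist has "Complete the Cognition (MoCA) test (pre-intervention) (Primary Outcome; Appendix J" at the first session and "Complete the Cognition (MoCA) test (post-intervention, if not completed during the Pre-Last Visit) (Primary Outcome; Appendix J" at the twelfth session, in Week 4. The baseline test may also be done at a visit just before Week 1, and the final one just before the last session.

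A modified MoCA or a different cognitive test is allowed where aphasia, hemiopsia, other deficits or demographic factors prevent accurate testing. That provision is about whether a person can be tested. It does not address practice.

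The study has one cohort ("We will recruit 20 stroke survivor dyads (n=40) from the" several clinics and support groups). Randomised comparison is left to later work: "the expected outcomes are to develop randomized control trials (RCTs) to determine the effectiveness of the Oculus VR for stroke rehabilitation". For S.A.2, the Statistical Analysis section plans a paired t-test or Wilcoxon signed rank test of the difference score and treats Cohen's d as an early indication of how effective the headset is. It adds that inference is not the main interest of the pilot. The Intervention section expects the effect estimate to inform randomised trials. Retest effects are not mentioned.

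**The concern.** A person who has already heard the five words, copied the drawing and repeated the sentences may score higher the second time with no change in cognition. With a control group tested on the same schedule, such a gain would appear in both arms and cancel on average. Here it would pass unadjusted into the mean change, the significance test and Cohen's d, and it would favour the intervention.

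The MoCA is the only cognitive outcome scheduled before and after the intervention. If its d is labelled effectiveness and carried forward, a later randomised trial could be sized on an effect that is partly, or wholly, familiarity with the test.

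**Working it through.** The documents give no MoCA standard deviation, target effect, alpha or power, so there is no planned figure to reproduce. The check has two parts.

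**Comparison of the documents.** Appendix J contains one form. Table 1 and Appendix Q both point to it before and after the intervention. No passage names a second version, and none describes a comparison group or an adjustment for retesting. Re-use of the form is therefore the natural reading, though it is inferred.

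**Illustration of what a retest shift would do.**

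Inputs from the documents:
- n = 20 stroke survivors.
- Test-retest correlation r = .92 (Appendix A).

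Assumed inputs:
- MoCA SD of 3 or 4 points.
- A lower correlation of .70 as the other end of the range, because eligibility restricts the spread of scores.
- Two-sided alpha of 0.05.
- No true effect.
- A retest shift of 0.25, 0.5 or 1 point.

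Formulas:
- SD of change = SD × √(2(1 − r)).
- d on the change SD = shift ÷ SD of change.
- d on the baseline SD = shift ÷ SD.
- Probability of significance: noncentral t with 19 degrees of freedom and noncentrality d × √20, where d is on the change SD.

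For example, with SD 3 and r = .92, the SD of change is 3 × √0.16 = 1.20. A 1-point shift gives d = 1 ÷ 1.20 = 0.83 and noncentrality 0.83 × 4.47 ≈ 3.7.

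| r | SD | SD of change | 0.25 point | 0.5 point | 1 point |
|---|---|---|---|---|---|
| .92 | 3 | 1.20 | 14% | 42% | 94% |
| .92 | 4 | 1.60 | 10% | 26% | 76% |
| .70 | 3 | 2.32 | 7% | 15% | 45% |
| .70 | 4 | 3.10 | 6% | 11% | 28% |

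The last three columns give the probability of p < 0.05 with no true effect. With no shift it is 5%.

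For a 1-point shift, d is 0.32-0.83 on the change SD and 0.25-0.33 on the baseline SD. The plan does not say which SD it will use.

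The smallest significant mean change is 2.093 ÷ √20 = 0.468 change SDs. At SD 3 and r = .92 that is 0.468 × 1.20 = 0.56 points, a little over half of one recall word.

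The reported r = .92 does not rule out a retest gain. A correlation is unchanged when every score rises by the same amount. A high r also narrows the SD of change, so a small shift is more easily detected.

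**The case against.** The strongest reply is that the harm is not shown. No sentence says that the same word list is given twice. A reader might infer that learning the test will be counted as improvement, but the documents do not show that any learning occurs. Most entrants have mild to moderate cognitive impairment and may retain little after 3-4 weeks. Those admitted with normal cognition start near the 30-point ceiling and have little room to gain. This stands: the supportable claim is that a retest gain cannot be separated from improvement.

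The illustration also rests on assumed shifts and SDs. The 94% comes from the least favourable corner, and the r of .92 comes from an instrument source and not from this restricted sample. This stands too, and a 0.25-point shift gives only 6-14%.

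The plan describes itself as a pilot, calls the d preliminary, and attaches no go/no-go rule to the MoCA. That lowers the stakes. It does not settle the matter, because the test is kept, the d is still described as a measure of effectiveness, and the estimate is meant to inform randomised trials.

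Finally, retesting is one of several uncontrolled influences, alongside concurrent therapy, home exercises and regression to the mean after screening on the MoCA. A second form would not make the d a measure of effectiveness. That is correct, and it is why the change in reporting is needed whether or not another form is available.

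**Conclusion.** The point holds as a limit on interpretation. As written, the plan cites one fixed form at both assessments, has no control group, and interprets the resulting d as preliminary effectiveness. The estimate is open to an upward retest bias that the study cannot detect or remove.

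The size of that bias is unknown. Under the stated assumptions, the chance of a significant result with no true effect runs from 6% for a 0.25-point shift to 94% for a 1-point shift. That width shows how much the conclusion depends on a quantity the study does not measure. It is not evidence that a shift of any given size will occur.

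The conclusion rests on reading the single form in Appendix J, cited twice, as the form used twice. If another version is intended, the protocol should say so. Participants given a modified MoCA or a different test are an exception. The primary objective of feasibility, usability and acceptability is not affected.

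**What to change.** **Reporting, in any case.** Amend the S.A.2 paragraph of the Statistical Analysis section so that the MoCA change and its Cohen's d are described as an uncontrolled pre-post change that includes retest effects. Remove the description of this d as a measure of effectiveness, and state that it will not be used unadjusted to plan a randomised trial. The cost is a few sentences.

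**Test form, where still possible.** For participants not yet tested, and if the site has another MoCA version (the documents do not say), use it at one of the two assessments. Alternate the order of the two versions across participants and record which was given each time. The restriction matters: the document is dated 03/06/2024 while the stated study duration ends in October 2023, so some or all testing may already be complete. The cost is a second form and one recorded field. Versions may differ slightly in difficulty. Alternating the order balances this on average but adds some variance.

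**Optional sensitivity row.** The change excluding delayed recall (30 − 5 = 25 points) can be shown descriptively from existing item scores. It should carry a note that it leaves practice on the other repeated items and may discard real memory gain, since Appendix C lists memory among the functions the game exercises. It should not replace the total score.
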